6.2 Treatment Regimens

There are 2 single -blind treatment groups: abatacept 125mg SC weekly or adalimumab 40mg SC biweekly, both with concomitant MTX therapy.

There is one open-label treatment group defined: abatacept 125mg SC weekly with concomitant MTX therapy.

6.3 Populations for Analyses

The as-treated analysis population will contain all randomized subjects who received at least one dose of single-blind study medication, and subjects will be grouped on an as-randomized basis unless the subject received the incorrect medication for the entire period of single-blind treatment. In that case, the subject will be analyzed in the treatment group associated with the incorrect medication they received. This population will be used for all analyses of the single blind period, including demography, baseline disease characteristics, biomarker, efficacy safety and immunogenicity analyses and for the Week 48 efficacy and biomarker analyses.

The open-label abatacept population will contain all subjects treated with open-label abatacept.

The cumulative abatacept population will contain all subjects treated with single-blind and/or open-label abatacept.

7 STATISTICAL ANALYSES

7.1 General Methods

All the analyses, with the exception of the analysis for efficacy responder rate, will be 'as-observed', ie. the available data will be used and there will be no imputation for missing values. For the efficacy responder rate analysis a non-responder imputation will be applied for missing data.

In [APPENDIX 1](#) the list of biomarkers is shown. The different biomarkers are classified into different biomarker categories (category 1 up to 12). The biomarker results (tables and plots) will be provided for each of these biomarker categories separately.

The focus of the exploration will be on Day 169 analysis. However, mean or median changes from baseline (with 95 % CI) over time from day 1 to day 169 of the single-blind period will be displayed for all biomarkers. These plots will be grouped by biomarker category (see [APPENDIX 1](#)).

All Day 337 analyses and analyses over time from day 1 to day 337 (efficacy and biomarkers) will be provided by original randomized treatment and grouped by biomarker category if applicable (see [APPENDIX 1](#)).

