2 STUDY DESCRIPTION

2.1 Study Design

This is an exploratory, randomized, single-blinded assessment study in subjects with early RA defined as symptoms of RA for no more than 12 months prior to screening and satisfying the criteria for RA according to the ACR/EULAR 2010 classification at some point during the 12-month period. Eligible subjects must have been on methotrexate (MTX) for at least 12 weeks with a stable dose of MTX for at least 28 days prior to randomization and are naive to biologic DMARD. The study consists of a screening period of up to 28 days, followed by a 24-week single-blind treatment period with abatacept or adalimumab, followed by a 24-week open-label treatment period with abatacept, followed by an 85-day follow-up period.

Eligibility will be based on specified inclusion and exclusion criteria, medical history, disease activity and safety assessments. Randomization must occur within 28 days of signing the informed consent.

On Day 1, subjects will be randomized to one of two parallel treatment arms in a 1:1 ratio:

- abatacept SC (125mg) weekly
- adalimumab SC (40mg) once every two weeks

All subjects continuing in the open-label treatment period will receive abatacept 125mg SC, weekly. Those subjects randomized to adalimumab will switch to abatacept at Week 28 following a six week washout period. The dose of methotrexate must remain stable throughout the study and may only be lowered due to intolerance or adverse event. Subjects not wishing to continue on open-label abatacept have the option of discontinuing treatment at the end of the single-blind period and proceeding to the post-treatment follow-up period.

Subjects who discontinue treatment of study drug or complete the study will have one follow-up visit 85 days after the last dose of investigational product to perform safety assessments.

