8.3 Missing Measurements

For listings of efficacy measures or biomarkers, missing values will be represented as missing. For analyses involving efficacy or biomarkers, missing values will not be imputed.

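### Day 337 mean changes are labelled as-treated but can come only from subjects who chose open-label abatacept, so the Week 24 step and by-arm differences can reflect selection

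*SAP*

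**What the plan says.** - **Grouping.** SAP 7.1: "All Day 337 analyses and analyses over time from day 1 to day 337 (efficacy and biomarkers) will be provided by original randomized treatment".
- **Missing data.** For everything except responder rates, SAP 7.1 says "the available data will be used and there will be no imputation for missing values". The exception is: "For the efficacy responder rate analysis a non-responder imputation will be applied for missing data". SAP 8.3 gives the rule without that exception: "For analyses involving efficacy or biomarkers, missing values will not be imputed".
- **Population.** SAP 6.3 assigns the as-treated population (randomized, at least one single-blind dose) to the single-blind analyses "and for the Week 48 efficacy and biomarker analyses". It also defines an open-label population, which SAP 7.4.1 uses for exposure by original arm.
- **Entry.** SAP 2.1: "Subjects not wishing to continue on open-label abatacept have the option of discontinuing treatment at the end of the single-blind period". On treatment: "All subjects continuing in the open-label treatment period will receive abatacept 125mg SC, weekly". For the other arm: "Those subjects randomized to adalimumab will switch to abatacept at Week 28 following a six week washout period".
- **Usable data.** SAP 8.5 drops efficacy and biomarker assessments made more than 42 days after the last dose. The Week 48 window is Day 310 to 365. For adalimumab subjects who enter open label, the Week 24 window closes 10 days after the last single-blind dose.
- **Reporting.** SAP 7.3.1 tabulates the number treated in open label, and discontinuations with reasons. The visible text describes no comparison of entrants with decliners.

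**The concern.** A Day 1 to Day 337 curve by original arm reads as one cohort followed over time. Here the earlier points draw on single-blind subjects generally and the later ones only on those who agreed to continue. The choice also differs between arms: continuing means the same drug in one arm, and a washout and a change of drug in the other. A subject doing well on adalimumab may have a reason to decline that a subject doing well on abatacept does not have.

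If entry is related to response, a curve can bend after Week 24 with no change in any individual. If the relation differs by arm, an arm difference at Day 337 can also arise from selection. Either could be read as an effect of switching, or of longer abatacept treatment, on the immune profile. Responder rates are largely outside this point, provided that SAP 7.1's non-responder rule governs and not SAP 8.3.

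**Working it through.** **1. The plan's own threshold (SAP 5).** Smallest significant standardized difference = t × √(2/n).
- n = 25 per arm: 2.011 × √(2/25) = 0.569 (plan: 0.57).
- n = 40 per arm: 1.991 × √(2/40) = 0.445, or 0.438 with the normal critical value (plan: 0.44).

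Both figures reproduce.

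**2. Who can contribute at Day 337.** Protocol 4.5.1 puts the last single-blind abatacept dose at Day 162. Protocol 4.5.2 puts the last adalimumab dose at Day 152, while 14-day steps from Day 1 give 1 + 11 × 14 = Day 155, so both are carried.
- Abatacept decliner: 162 + 42 = Day 204.
- Adalimumab decliner: 152 + 42 = Day 194, or 155 + 42 = Day 197.

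The follow-up visit in Protocol Table 5.1-3 collects only safety items and a pregnancy test. No decliner can reach Day 310 to 365. For mean changes, the as-treated population at Day 337 is in practice the entrants who still have data.

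**3. The Week 24 value of adalimumab entrants.** The window closes at 152 + 10 = Day 162, or 155 + 10 = Day 165. Protocol Table 5.1-2 allows 3 days either side of the visit, so Day 166 to 172. An entrant who doses and attends on schedule can fall outside the window, while a decliner's value stays in (window to Day 211). SAP 7.7.1 records a later change from 10 to 20 days, but for adverse events; SAP 8.5 still says 10.

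**4. Size under assumptions.** The documents give no entry rate and no link between entry and response. Assume 40 per arm, SD 1, no true difference, and entry probability expit(1.1 ± kY). Here Y is the Day 169 change, the sign is opposite in the two arms, and Day 337 has correlation ρ with Day 169.

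Mean of Y among entrants: m(k) = E[Y·expit(1.1 + kY)] / E[expit(1.1 + kY)]. Spurious arm difference at Day 337 = 2ρ·m(k).

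| k | Entry | m(k) | ρ = 0.3 | ρ = 0.5 | ρ = 0.7 |
|---|---|---|---|---|---|
| 0.5 | 74% | 0.124 | 0.075 | 0.12 | 0.17 |
| 1.0 | 71% | 0.242 | 0.14 | 0.24 | 0.34 |

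The range is about 0.08 to 0.34 SD. Each arm's own Day 337 mean moves by half of that. In simulation a nominal 5% test rejects 8% and 15% of the time at ρ = 0.5, and 11% and 25% at ρ = 0.7.

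**5. The matching threshold.** 40 × 0.74 = 29.6 and 40 × 0.71 = 28.4, so about 29 entrants per arm: 2.003 × √(2/29) = 0.53 SD. The plan's 0.44 is for 40 per arm and is not the right comparator here.

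**6. Other inputs.**
- Opposite directions, 80% entry, ρ = 0.5: 0.08, 0.13 and 0.19 SD for entry odds ratios of 1.5, 2 and 3 per SD.
- Opposite directions, entry 70 to 95%, ρ 0.3 to 0.7, odds ratio 1.5 to 3: 0.01 to 0.38 SD.
- Same direction, entry 90% against 70%, ρ = 0.5: 0.06 SD (odds ratio 2) and 0.09 SD (odds ratio 3).
- Same direction and equal entry, or entry unrelated to response: 0.00 SD.

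**7. Does the remedy work?** At ρ = 0.7, a likelihood estimate using everyone's Day 169 value had bias 0.01 (k = 0.5) and 0.00 (k = 1.0), against 0.18 and 0.34 as-observed in the same simulation. Its SD was no larger (0.246 against 0.257; 0.252 against 0.259). In this simulation entry depends only on the observed Day 169 value, so missing at random holds by construction.

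**The case against.** A reader might infer that the Day 337 contrast is biased, and in opposite directions in the two arms. The documents do not show that. They give no entry rates, no reasons for declining and no direction, and step 6 includes cases with no bias at all. This stands: the claim is that the contrast can be biased.

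A reader might also take a larger size. If Day 337 equalled Day 169 for every subject, the same inputs would give 0.25 to 0.48 SD and 16 to 48% rejection. That is hard to defend for an arm that goes through a washout and changes drug. Even 0.48 SD is below the matching threshold of 0.53. Biomarker bias shrinks further if entry follows clinical response and the biomarker is only loosely tied to it.

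SAP 7.5 and 7.6 are not in the public text. A model, a display of n per visit or an entrant-only analysis may be specified there, and no Day 337 test is visible. Nor are the amendments that created the open-label period available. So the absence of a safeguard cannot be asserted for the full plan. What remains is that the general rules in SAP 6.3, 7.1 and 8.5 produce the change of cohort, and the visible text does not flag it.

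The study is exploratory, has no primary or secondary endpoint, and focuses on Day 169. That lowers the stakes but does not make a two-arm curve to Day 337 safe to read.

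Entrant-only curves still condition on a choice made after randomization. They remove the change of cohort at Week 24, not the selection between arms. The fix has to say so.

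**Conclusion.** The point holds in a limited form. It is certain from the stated rules that, for mean changes, decliners leave the analysis after Week 24 and that the Day 337 label (as-treated) does not describe the contributing subjects. It is conditional that this distorts results: a within-arm step needs entry to depend on response, and a by-arm difference needs that dependence or the entry rates to differ between arms. Under the assumed opposite-direction selection the difference is about 0.08 to 0.34 SD, which is a material part of the 0.53 SD needed for significance but below it. The assumptions are ours and the lower end is negligible. The change is worth making before the Day 337 results are produced. It gives no reason to doubt the Day 169 focus of the study, apart from the window problem in step 3.

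**What to change.** 1. **SAP 8.5, first.** Reconcile the Week 24 analysis window for adalimumab entrants (last dose plus 10 days, about Day 162 to 165) with the Day 169 ± 3 visit, so that their Week 24 values are retained. Items 2 and 3 both rely on those values.
2. **SAP 6.3 and 7.1.** Show the Day 1 to Day 337 mean-change curves and the Day 337 changes in open-label-treated subjects by original arm, with n at each visit. Tabulate Week 24 values of entrants and decliners by arm. State that the curves describe entrants and that arm differences among them are not protected by randomization.
3. **SAP 7.1.** If any by-arm Day 337 contrast of a continuous measure is reported, add as a sensitivity analysis a repeated-measures likelihood estimate from all visits of all as-treated subjects. State that it assumes missing at random given the observed visits, and that it targets the outcome had all subjects continued to abatacept.
4. **SAP 7.1 and 8.3.** Make the two statements on imputation for responder rates agree.

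Cost: SAP wording, one table per measure, and a model only where a contrast is reported. With twelve biomarker categories that is real programming work, but it needs no new data. The long curves lose some subjects in their Day 1 to Day 169 part. The separate single-blind curves are unaffected by items 2 and 3; item 1 can change their adalimumab Week 24 point.

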7.2 Study Conduct

As this study includes only exploratory objectives, relevant protocol deviations will not be assessed.

7.3 Study Population

Frequency distributions or summary statistics of data pertaining to subject disposition, demographics, baseline characteristics, and medical history will be tabulated and displayed by treatment group. No statistical test will be carried out for comparison of any baseline measures among treatment groups

7.3.1 *Subject Disposition*

The number of subjects enrolled into the study at screening, the number of subjects randomized, the number of subjects who received at least 1 dose of single-blind study medication (abatacept or adalimumab), and the number of subjects who discontinued during the single-blind treatment period, together with reasons for discontinuation taken from the eCRF status page, will be summarized. The summary will also present the number of subjects treated in the OL period.

In addition, the number of subjects treated in open-label abatacept period, and the number of subjects who discontinued during the OL abatacept treatment period, together with reasons for discontinuation taken from the eCRF status page will be summarized.

7.3.2 *Demography and Baseline Characteristics*

Demographic, baseline disease characteristics and biomarkers at baseline of all randomized subjects who received at least one dose of study medication will be summarized. For continuous variables, they will be summarized using means, standard deviations, median, quartiles and ranges. The distribution of categorical variables will be summarized by treatment group using frequencies and percentages.

Baseline demographic characteristics include the following:

- age in years
- weight in kg
- gender
- race
- geographic region

Baseline disease characteristics include:

- duration of disease in months
- number of tender joints (28)
- number of swollen joints (28)
- number of tender joints (68)
- number of swollen joints (66)
- pain
- HAQ-DI
- subject assessment of disease activity
- physician assessment of disease activity
- CRP
- Rheumatoid factor status
- DAS28-CRP
- SDAI
- CDAI

In addition, all the biomarkers will be summarized at baseline.

7.3.3 *Medical History and Prior Medication*

Medical history and prior anti-rheumatic medication information will be summarized by treatment group using frequencies for all subjects in the as-treated analysis population.

7.4 *Extent of Exposure*

7.4.1 *Study Therapy*

Extent of exposure to single-blind study drug (abatacept and adalimumab) in the as-treated analysis population will be summarized in two ways; first, by the number of study drug doses, summarizing frequency distribution of number of study drug doses by treatment group, and second, by the number of days the subject is known to be on study drug, ignoring any dosing interruptions.

For subjects who are not treated in the open-label period, exposure to single-blind study drug in days is calculated as:

- exposure = (date of last single-blind study medication - date of first single-blind study medication +1) + 56.

The offset of 56 days represents approximately four times the half-life of abatacept in humans.

For subjects who receive single-blind abatacept study drug and enter the open-label period within 56 days of the last dose of single-blind study medication, exposure to single-blind study drug in days is calculated as:

- exposure = (date of first open-label study medication - date of first single-blind study medication).

For subjects who receive single-blind adalimumab study drug, exposure to single-blind study drug in days is calculated as:

- exposure = (date of last single-blind study medication +10 - date of first single-blind study medication).

To align the exposure of adalimumab with the exposure of abatacept and taking into account that for adalimumab there is a wash-out period of 6 weeks, 10 days is used to adjust the exposure for adalimumab. Ten (10) is equal to the expected maximum number of days after last single-blind abatacept dose and prior to the first open-label abatacept dose (7 days +/- 3 days).

Extent of exposure to abatacept (single blind and open-label) during the cumulative abatacept period will be summarized in two ways; first, by the number of abatacept injections, and second, by the number of days the subject is known to be on abatacept, ignoring any dosing interruptions.

$$\text{exposure} = (\text{date of last abatacept dose} - \text{date of first abatacept dose} +1) + 56.$$

The offset of 56 days represents approximately four times the half-life of abatacept in humans.

Abatacept includes single-blind abatacept and open-label abatacept. Exposure will be summarized for cumulative abatacept population and presented for all subjects in this population combined

Extent of exposure to abatacept during the open-label abatacept period will be summarized in two ways; first, by the number of abatacept injections, and second, by the number of days the subject is known to be on abatacept, ignoring any dosing interruptions.

- exposure = (date of last OL abatacept dose - date of first OL abatacept dose +1) + 56.

The offset of 56 days represents approximately four times the half-life of abatacept in humans.

Exposure will be summarized for the open-label population by the original randomized treatment groups and for all OL treated subjects combined.

[figure not shown]

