### 3. Age and Reproductive Status

- a) Men and women, ages  $\geq$  18 years (or age of majority)
- b) Women of childbearing potential (WOCBP) must have a negative serum or urine pregnancy test (minimum sensitivity 25 IU/L or equivalent units of HCG) within 24 hours prior to the start of study drug.
- c) Women must not be breastfeeding and must agree not to breastfeed during the study and for 100 days thereafter
- d) WOCBP must agree to follow instructions for method(s) of contraception for the duration of treatment with study drug plus 5 half-lives of study drug (70 days) plus 30 days (duration of ovulatory cycle) for a total of 100 days post-treatment completion.
- e) Males who are sexually active with WOCBP must agree to follow instructions for method(s) of contraception for the duration of treatment with study drug, plus 5 half-lives of the study drug (70 days) plus 90 days (duration of sperm turnover) for a total of 160 days post-treatment completion.
- f) Azoospermic males and WOCBP who are continuously not heterosexually active are exempt from contraceptive requirements. However they must still undergo pregnancy testing as described in this section.

Investigators shall counsel WOCBP and male subjects who are sexually active with WOCBP on the importance of pregnancy prevention and the implications of an unexpected pregnancy. Investigators shall advise WOCBP and male subjects who are sexually active with WOCBP on the use of highly effective methods of contraception. Highly effective methods of contraception have a failure rate of  $< 1\%$  when used consistently and correctly.

At a minimum, subjects must agree to the use of **two methods** of contraception, with one method being highly effective and the other method being either highly effective or less effective as listed below:

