### **3.6.2      *Lost to Follow-Up***

All reasonable efforts must be made to locate subjects to determine and report their ongoing status. This includes follow-up with persons authorized by the subject as noted above. Lost to follow-up is defined by the inability to reach the subject after a minimum of three documented phone calls, faxes, or emails as well as lack of response by subject to one registered mail letter. All attempts should be documented in the subject's medical records. If it is determined that the subject has died, the site will use permissible local methods to obtain the date and cause of death.

If investigator's use of third-party representative to assist in the follow-up portion of the study has been included in the subject's informed consent, then the investigator may use a Sponsor-retained third-party representative to assist site staff with obtaining subject's contact information or other public vital status data necessary to complete the follow-up portion of the study. The site staff and representative will consult publicly available sources, such as public health registries and databases, in order to obtain updated contact information. If after all attempts, the subject remains lost to follow-up, then the last known alive date as determined by the investigator should be reported and documented in the subject's medical records.

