7.7.6 *Multiple Adverse Events*

Several descriptive summaries of adverse events that takes into account the number of occurrences that an AE was reported by individual patients will be provided. In order to prepare these summaries, the CRF data will be processed according to standard BMS algorithms to categorize each line of patient data as a new occurrence or a continuation of an existing event. This

determination will be based upon onset and resolution dates. Each line of patient data will represent the maximum severity observed as well as the last known assessed relationship to study medication by the investigator.

This data will be presented as the rate per 100 years of patient exposure. Exposure to study medication will be calculated according to approved standard BMS algorithms as well.

As an example, if 5 patients report 7 unique episodes of headache and had a combined cumulative exposure of 20 years to study medication, the incidence rate is reported as $7 / 20 * (100)$ or 35 cases per 100 patient years of exposure.

The following summary tables will be provided:

- A table showing the total number and rate (exposure adjusted) of occurrences for all AEs occurring in at least 10% of the subjects treated will be presented for the single-blind period.
- Listing displaying the unique instances of all AEs, i.e., after duplicates have been eliminated and overlapping and contiguous occurrences of the same event have been collapses.

Similar summaries and listings will be done for the cumulative abatacept period.

7.7.7 *Summaries of Laboratory Data*

Safety summaries based on laboratory test results include evaluation of laboratory abnormalities and change in laboratory test values from baseline. The baseline value on a per analyte basis is the last non-missing value prior to the start of single-blind study drug

Laboratory abnormalities are identified using a pre-defined set of marked abnormality criteria. The criteria will be listed in the CSR. The frequencies of laboratory abnormalities will be presented by laboratory test and treatment group during the single-blind treatment period and by laboratory test and all abatacept subject combined into one group for the cumulative abatacept period. The single-blind treatment period and the cumulative abatacept period for the laboratory analyses are defined in [Section 6.1](#).

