9 CONTENT OF REPORTS

At the time of the first lock when the last randomized subject completes the 24 week single-blind treatment period, the analyses described in this SAP, with the exceptions of the analyses for the biomarker categories 2, 3 and 5 in [APPENDIX 1](#), will be performed. The results of these analyses will be presented in a standard BMS Clinical Study Report (CSR).

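### Three of the five exposure formulas in SAP 7.4.1 credit 56 days after the last dose even when the subject was not observed for them

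*SAP*

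**What the plan says.** SAP 7.4.1 summarises exposure "by the number of days the subject is known to be on study drug, ignoring any dosing interruptions". It gives five formulas:

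- **Single-blind, not treated in open label:** "exposure = (date of last single-blind study medication - date of first single-blind study medication +1) + 56".
- **Single-blind abatacept, entering open label within 56 days:** "exposure = (date of first open-label study medication - date of first single-blind study medication"), with no 56-day offset.
- **Single-blind adalimumab:** last dose + 10 days minus first dose, with no 56-day offset and no condition about entering open label.
- **Cumulative abatacept:** last minus first abatacept dose, + 1, + 56.
- **Open-label:** last minus first open-label dose, + 1, + 56.

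The reason given for the offset is "The offset of 56 days represents approximately four times the half-life of abatacept in humans". No formula mentions death, loss of contact or data cut-off.

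SAP 6.1 counts adverse events and laboratory results to 56 days after the last dose for subjects who do not enter open label, and for the open-label and cumulative periods. SAP 7.7.6 says of multiple adverse events: "This data will be presented as the rate per 100 years of patient exposure". It takes exposure from the sponsor's standard algorithms, which are not reproduced, and does not point to 7.4.1.

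**The concern.** Days on which a subject is dead, out of contact or beyond the data cut-off are not days known to be on drug, and no event can be recorded on them. Protocol 3.6 says that subjects who withdraw consent or are lost are not followed further. For them the fixed 56 days can be empty person-time.

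Two outputs are at stake. The exposure summaries in 7.4.1 are too large for these subjects whatever else is done. If the same exposure is the denominator in 7.7.6, rates per 100 patient-years come out too low, most of all in the group that loses more subjects from observation early.

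**Working it through.** **1. The plan's own figures.** Protocol 3.3.1 (age and reproductive status) has "plus 5 half-lives of study drug (70 days) plus 30 days", so one half-life is 70/5 = 14 days and four are 4 × 14 = 56 days. The offset is reproduced. The worked rate in SAP 7.7.6 also holds: 7/20 × 100 = 35 per 100 patient-years.

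**2. Per subject.** Take the first dose on Day 1, and let d be the days observed after the last dose.

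- SAP formula: E = (last − 1 + 1) + 56 = last + 56.
- Capped: E* = last + min(56, d).
- Overstatement: 56 − min(56, d), which is zero once d reaches 56.

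Protocol 4.5.1 puts the last scheduled abatacept dose on Day 162. SAP 8.5 gives Week 24 a target of Day 169. Day 57 is the Week 8 target. The values of d are illustrative.

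| Last dose | d | E | E* | Exposure | Rate, if built on E |
|---|---|---|---|---|---|
| Day 162 | 0 | 218 | 162 | +34.6% | −25.7% |
| Day 162 | 7 (lock on Day 169) | 218 | 169 | +29.0% | −22.5% |
| Day 162 | 28 | 218 | 190 | +14.7% | −12.8% |
| Day 57 | 0 | 113 | 57 | +98.2% | −49.6% |
| Day 57 | 28 | 113 | 85 | +32.9% | −24.8% |
| any | 56 or more | last + 56 | last + 56 | 0 | 0 |

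**3. Per arm, single-blind.** SAP 5 gives 40 subjects per arm after the increase. The documents do not give the number affected, so 1 to 8 is an assumption. The rest are taken as abatacept subjects entering open label, at 169 − 1 = 168 days.

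- Low end, 1 subject, last dose Day 57, d = 28: (113 + 39 × 168)/(85 + 39 × 168) = 6665/6637 = 1.004.
- High end, 8 subjects, last dose Day 57, d = 0: (8 × 113 + 32 × 168)/(8 × 57 + 32 × 168) = 6280/5832 = 1.077.

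A true rate of 35 would then be reported as 34.9 to 32.5, if the rate uses this exposure.

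**4. Cumulative abatacept.** Assume a last dose on Day 330, so 386 days are credited.

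- 2.5% of subjects cut short, d = 7: 386/(0.975 × 386 + 0.025 × 337) = 1.003.
- 20% cut short, d = 0: 386/(0.8 × 386 + 0.2 × 330) = 1.030.
- Every subject still on drug at the cut-off: 386/337 = 1.145 (d = 7) to 386/330 = 1.170 (d = 0).

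**5. Adalimumab.** A subject who does not enter open label meets the conditions of two formulas. They differ by (last − first + 1 + 56) − (last + 10 − first) = 47 days. For subjects who do enter open label, SAP 7.7.1 counts events to 20 days after the last dose, while 7.4.1 credits 10. With the last dose on Day 155 (1 + 11 × 14), that is 174 against 164 days, so a rate on this exposure would be about 6% too high. Protocol 4.5.2 prints Day 152 for Week 22, which gives 171/161, again about 6%.

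**The case against.** The best defence is that the 56 days are a pharmacological convention and equal the adverse event window in SAP 6.1. For anyone observed that long, numerator and denominator match by design. This stands, and it limits the error to subjects whose observation ends sooner.

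Several stronger readings are tempting but not supported:

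- **That every exposure formula is affected.** Two of the five add no 56 days. Read literally, the adalimumab formula may keep the offset out of that arm's single-blind exposure altogether.
- **That stopping treatment early inflates exposure.** Protocol 3.5 and 3.6.1 keep such subjects in follow-up, and both documents plan a visit 85 days after the last dose. Only death, withdrawal from follow-up, loss or a cut-off before day 56 matters.
- **That reported event rates are understated.** SAP 7.7.6 relies on a sponsor algorithm that the documents do not show. It may or may not cap. The summaries in 7.7.1 are proportions of treated subjects and use no person-time.
- **That cumulative exposure is inflated by more than a quarter.** SAP 9 schedules the analyses "At the time of the first lock when the last randomized subject completes the 24 week single-blind treatment period" and exempts only some biomarker categories. Running the cumulative tables then, with an assumed mean of 200 observed days, would give 256/200 = 1.28 and rates 22% too low. But the 200 days are not in the documents, and SAP 7.7 separates the Week 24 analyses from the cumulative period. The note in 7.7.1 on the 20-day threshold also shows that the single-blind analysis had been run before this SAP version was written. No cut-off for the cumulative tables is given.

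**Conclusion.** The gap is real and minor. Followed as written, three of the five formulas overstate exposure by up to 56 days for each subject who dies, withdraws from follow-up, is lost or reaches the data cut-off within 56 days of the last dose. The error in those formulas goes one way only.

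At arm level it is probably small: about 0.4% to 7.7% for single-blind exposure if 1 to 8 of 40 subjects are affected, and about 0.3% to 3.0% for cumulative exposure if 2.5% to 20% are cut short. It would reach about 15% to 17% only if everyone were still on drug at the cut-off. All these figures rest on the stated assumptions about numbers and dates. A downward bias in the 7.7.6 rates is conditional on those rates using the 7.4.1 exposure. The adalimumab overlap and the 10-day versus 20-day windows are separate inconsistencies, and the second biases in the opposite direction.

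**What to change.** 1. In SAP 7.4.1, end exposure in the three affected formulas at the earliest of last dose + 56 days, death, last study contact or assessment at which adverse events could be recorded, and data cut-off.
2. In SAP 7.7.6, state that this exposure, matched to the adverse event counting window, is the denominator.
3. Reconcile the adalimumab last dose + 10 formula with the + 56 formula for subjects who do not enter open label, and with the 20-day window in SAP 7.7.1.

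The last known alive date should not serve as the cap. Protocol 3.6.2 asks that "the last known alive date as determined by the investigator should be reported and documented", but only for subjects who remain lost and in the medical records, and it allows public sources to be consulted. Knowing that a subject is alive is not the same as observing adverse events.

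The cost is a few lines of SAP text, a small programming change, and a check that a last-contact date is available in the database. Stated exposure becomes slightly lower, and any rate built on it slightly higher.
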